#### 9.3.2.2.1. Statistical Analysis of the Primary Endpoint Change in Plasma Glucose during Exercise

Changes in plasma glucose will be compared between Lyumjev versus Humalog from the start to the end of exercise during either 50% or 100% reduction of basal infusion rates.

For the primary endpoint, the change in plasma glucose will be analyzed using a mixed-effect model that includes treatment (Lyumjev, Humalog), sequence, period, and treatment as fixed effects and participant within sequence as a random effect. LSmeans, treatment differences in LSmeans, and the corresponding 90% CIs for the treatment differences will be estimated from the model. The p-value on the difference between LSmeans will be used to determine statistical significance.

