4. STUDY OBJECTIVES AND ENDPOINTS

4.1 **Primary Objective and Endpoint**

The primary objective of the study is:

• To compare changes in plasma glucose (PG) levels with LyumjevTM versus Humalog[®] from the start to the end of 60 minutes of moderate-intensity aerobic exercise using either 50% or 100% reduction of basal infusion rates, set 60 minutes or 15 minutes before the onset of exercise, respectively.

The primary endpoint of the study is:

• Changes in PG from the start to the end of exercise.

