9.4 Pharmacodynamic Assessment

9.4.1 Pharmacodynamic Analysis

Blood Ketones and Free Fatty Acids

Blood ketones and free fatty acids data will be summarized by timepoint and treatment, and listed.

Glucodynamic Parameter Estimation

Glucodynamic data will be determined from the plasma glucose (PG) reported from the YSI glucose analyzer during the exercise and MMTT assessment.

Glucodynamic data will be analyzed for the participants during each exercise and MMTT assessment. During the exercise period, the change from baseline value (the 0-hour time point prior to the start of exercise) for each participant will be calculated to derive the change in PG level from start to end of exercise.

The rate of PG during the exercise, the nadir PG, decremental AUC, for each exercise assessments will be calculated.

During the MMTT, the change from baseline values CCI

for each participant will be calculated. The approach used will be documented in the CSR.

The area under the baseline subtracted PG concentration versus time curve (incremental) (iAUC) will be calculated during the MMTT for each in-house periods; the list of derived iAUCs are:

- The incremental AUC from time zero to 30 minutes postmeal (iAUC0-30min)
- The incremental AUC from time zero to 1-hour postmeal (iAUC0-1hour)
- The incremental AUC from time zero to 2-hours postmeal (iAUC0-2hour)
- The incremental AUC from time zero to 3-hours postmeal (iAUC0-3hour)
- The incremental AUC from time zero to 4-hours postmeal (iAUC0-4hour)

In addition, the change from baseline maximum PG observed during the 4 hours postmeal $(\Delta PGmax)$ and change from baseline 1-hour plasma glucose $(\Delta PG1h)$ and 2-hour plasma glucose after the start of the meal $(\Delta PG2h)$ will be calculated. Other partial iAUCs may be calculated, as deemed appropriate.

The mean data will be presented by summary statistics and presented by treatment for those participants who received both treatments (Lyumjev and Humalog) with the same insulin dose (bolus dose for the MMTT or basal reduction) and meal consumption. The data will also be listed.

This will be the responsibility of Eli Lilly and Company.

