9.4.2 Pharmacodynamic Statistical Methodology

Primary glucodynamic endpoint

Changes in PG from the start to end of exercise will be statistically analyzed using a mixed– effect model. The model will include treatment (Lyumjev with 50% basal reduction, Lyumjev with 100% basal reduction, Humalog with 50% basal reduction, and Humalog with 100% basal reduction), sequence, period, timepoint, treatment-by-timepoint interaction as fixed effects, and participant-within-sequence as a random effect. Baseline (0 min timepoint) will be included as a covariate. The LS means, difference LS means between Lyumjev and Humalog for corresponding basal rate reduction, and corresponding 90% CIs, as well as the p-value, will be reported.

The p-value on the difference between LS means will be used to determine statistical significance.

Secondary glucodynamic endpoints

For the derived glucodynamic parameters iAUCs Δ PGmax, Δ PG1h, and Δ PG2h, a statistical analysis will be performed during exercise with a basal reduction, and after the MMTT independently. The modified full analysis population will be used for this analysis.

The parameters iAUCs during the MMTT and AUCs during exercise will be log-transformed before the statistical analysis. If negative values occur, the analysis will be performed on untransformed parameters. A mixed effects model will be used for this analysis. The model will include treatment (Lyumjev with 50% basal reduction, Lyumjev with 100% basal reduction, Humalog with 50% basal reduction, and Humalog with 100% basal reduction), sequence, and period as fixed effects, and participant-within-sequence will be included as a random effect. The LS means will be back-transformed to produce geometric means. The treatment geometric LS mean of each treatment, ratio of geometric means between Lyumjev and Humalog for corresponding basal rate reduction, and corresponding 90% CIs will be reported. The p-value will also be reported for the ratios. If the analysis is done on the untransformed parameters, the treatment LS means, difference in LS means between Lyumjev and Humalog for corresponding

basal rate reduction, and corresponding 90% CIs, as well as the p-value, will instead be reported. The treatment ratios and 90% CIs for the ratios will be calculated using the Fieller's theorem.

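### The SAP primary model uses one 0-minute glucose slope for every exercise timepoint, so the end-of-exercise contrast is adjusted with the wrong slope unless that slope is constant

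*SAP*

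**What the plan says.** The primary endpoint in SAP section 4 is "Changes in PG from the start to the end of exercise". SAP 9.4.1 defines the exercise response relative to the start value: "the change from baseline value (the 0-hour time point prior to the start of exercise) for each participant will be calculated".

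SAP 9.4.2 fits this response with the four product-by-reduction treatments, sequence and period, together with "timepoint, treatment-by-timepoint interaction as fixed effects, and participant-within-sequence as a random effect". It then states "Baseline (0 min timepoint) will be included as a covariate". The reported comparison is the "difference LS means between Lyumjev and Humalog for corresponding basal rate reduction", with a 90% CI and p-value.

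Three things are not stated there: which timepoints enter the response, whether minute 0 is one of them, and at which timepoint the LS means are compared. No interaction between baseline and timepoint is listed.

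The primary model in Protocol 9.3.2.2.1 lists "sequence, period, and treatment as fixed effects and participant within sequence as a random effect". It has no baseline covariate and no timepoint term, so it does not settle any of these.

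**The concern.** The model lets the product effect differ by timepoint but holds the effect of starting glucose constant across timepoints. The response is change from the same 0-minute value that serves as covariate. At minute 0 that change is zero whatever the starting value, so its slope on starting glucose is zero there. Later in the session the slope may be something else. A shared coefficient averages these slopes, while the endpoint needs the slope that applies at the end of exercise.

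At stake is how well the primary contrast is corrected for differences in starting glucose between a participant's paired sessions. Such differences can arise by chance. They can also arise because minute 0 is not a pre-treatment value: the study insulin has been running, and has covered three meals, since Day -1 (Protocol 4.1.3). Whatever the covariate fails to remove stays in the contrast as noise. If starting glucose differs systematically between products, it stays as a shift.

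**Working it through.** **The plan's own figure.** SAP section 7 gives 28 completers for about 80% power at 14 mg/dL, SD 27.9 mg/dL, two-sided alpha 0.10. Taking 27.9 as the SD of the paired difference (an assumption), n = [27.9 × (1.645 + 0.842)/14]² = 24.6, so 25; the noncentral t gives 26. Power at 28 is 82.7%. The figure is reproduced closely. It sets the scale below but does not bear on the slope question.

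**Set-up.** Let β(t) be the slope of change at minute t on 0-minute glucose, with β(0) = 0 by definition and β(60) = b. With complete data and equal weight for each timepoint, the shared slope is the average of β(t) over the modelled timepoints. Write it as f × b. If starting glucose differs by d between products, the minute-60 contrast keeps

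(1 − f) × b × d.

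**Inputs not readable in the documents.** The sampling times are blacked out, and neither b nor the spread of starting glucose is given. I take b = −0.3 and −0.6, d = 10 mg/dL, and several grids and slope shapes.

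| Slope shape and timepoints in the response | f | b = −0.3 | b = −0.6 |
|---|---|---|---|
| Linear growth, 0 to 60 by 10 | 0.50 | −1.50 | −3.00 |
| Linear growth, 10 to 60 by 10 | 0.583 | −1.25 | −2.50 |
| Linear growth, 20, 40, 60 | 0.667 | −1.00 | −2.00 |
| Square-root growth, 10 to 60 by 10 | 0.737 | −0.79 | −1.58 |
| Flat after minute 0, 0 to 60 by 10 | 0.857 | −0.43 | −0.86 |
| Flat after minute 0, minute 0 excluded | 1.00 | 0 | 0 |
| Strongest early (1.5b falling to b), 10 to 60 by 10 | 1.208 | +0.62 | +1.25 |

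Entries are mg/dL left in the end-of-exercise contrast. Example: (1 − 0.50) × (−0.6) × 10 = −3.0.

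**Simulation check.** The four SAP sequences were simulated with 28 participants, 1,500 replicates, participant as a block, and a within-participant SD of starting glucose of 17.7 mg/dL. At d = 10:
- Linear, minute 0 included: −1.4 (b = −0.3) and −2.8 (b = −0.6).
- Linear, minute 0 excluded: −1.2 and −2.3.
- Strongest early, minute 0 excluded: +0.4 and +1.2.
- With baseline-by-timepoint, or an ANCOVA on the end value alone, every result was within 0.3 of zero.

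A 40-replicate mixed-model fit with a random participant effect gave a shared slope of −0.30 against a true end slope of −0.60.

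**Precision when d = 0.** The shared-slope contrast was centred on zero. Its standard error against the interaction model, under linear growth:
- Minute 0 included: 4.78 v 4.69 (+1.9%) at b = −0.3; 4.89 v 4.68 (+4.5%) at b = −0.6.
- Minute 0 excluded: 4.69 v 4.65 (+0.9%); 4.95 v 4.81 (+2.9%).

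This agrees with the formula. The chance product difference in starting glucose has SD √2 × 17.7/√28 = 4.73 mg/dL. With f = 0.50 and b = −0.6 it leaves 0.5 × 0.6 × 4.73 = 1.42 mg/dL, and √(4.68² + 1.42²) = 4.89.

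**The case against.** **Direction is not established.** A reader might infer that a slope of zero at minute 0 proves the end contrast is under-adjusted. It does not. That requires minute-0 rows in the response or a slope that grows through exercise, and also LS means read at the end timepoint. The SAP states none of these. Naming the 0-minute value as baseline may mean that it is not a response row. Protocol 4.1.3 gives oral carbohydrate before exercise when glucose is below 90 mg/dL, which could make the slope strongest early and reverse the error. This stands. The remedy, however, works in either direction.

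**Averaged LS means.** If the LS means average over timepoints, the averaged slope is the matching adjustment. That is correct, but such an average is not the start-to-end change.

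**Power.** A reader might take the lost precision as a shortfall from the planned 80%. It is forgone gain. In the simulation at b = −0.6 with minute 0 included, the unadjusted standard error was 5.50, the shared-slope one 4.89 and the interaction one 4.68. Taking 27.9 as the unadjusted paired SD, f = 0.583, b = −0.5 and a within-participant SD of 20, the contrast variance is 27.9² − 0.25 × 800 + (0.417 × 0.5)² × 800 = 613, below the planning value of 778. Steeper slopes cost more: b = −0.7 with the same SD gives 17.6% extra variance over full adjustment, about 8% in standard error. That is the far corner of assumed values.

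**Bias.** Nothing in the readable text supports a 10 mg/dL product difference. The pre-exercise target, mealtime correction boluses and rescheduling all limit spread in starting glucose. A systematic difference caused by study insulin would itself be a treatment effect, so the remainder is bias only relative to the adjusted comparison that the SAP has chosen, not to the protocol's unadjusted change. This also stands.

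**Splitting the covariate.** A reader might go further and separate starting glucose into participant mean and session deviation. No document suggests that the two slopes differ, and the modified full analysis population admits participants with both products at only one basal reduction. I do not ask for it.

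**Conclusion.** The point holds in conditional form. As written, SAP 9.4.2 uses one 0-minute slope for all timepoints, and this is the right adjustment for the end-of-exercise contrast only if the slope is constant over the modelled timepoints. Under-adjustment is likely but not shown; the effect can vanish or reverse.

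The size is modest. With balanced starting glucose there is no bias on average, and the standard error is roughly 1% to 4.5% larger in the linear-growth scenarios simulated. At an assumed 10 mg/dL product difference in starting glucose, the error left in the contrast ranges from 0 to about 3 mg/dL in the under-adjusted direction, or about 1.2 mg/dL the other way in the early-slope case, against the 14 mg/dL design difference. These figures rest on assumed sampling times, slope shapes, b, starting-glucose SD and equal weighting of timepoints. They do not show that the trial is underpowered or its primary contrast materially biased. The case for acting is that the correction costs almost nothing and removes the dependence on an unstated constant slope.

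**What to change.** In SAP 9.4.2, primary glucodynamic endpoint:

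- List the timepoints that enter the response and exclude minute 0.
- Add a baseline-by-timepoint interaction, or replace the repeated-timepoint model with an ANCOVA on the end-of-exercise change alone.
- Name the end-of-exercise LS-mean difference between Lyumjev and Humalog, within each basal reduction, as the primary contrast.

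The interaction adds one parameter fewer than the number of modelled timepoints (five for an assumed six). No new data or participants are needed. In the simulations it lost essentially no precision even where the shared slope was already adequate.

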## 9.3.2.2.2. Statistical Analysis of the Secondary GD Endpoints

Changes in GD parameters during exercise and MMTT will be compared between Lyumjev versus Humalog during exercise with either 50% or 100% reduction of basal infusion rates.

Log-transformed iAUCs,  $\Delta PG_{max}$ ,  $\Delta PG1h$ , and  $\Delta PG2h$  will be evaluated to estimate geometric means, ratios of geometric means of insulin lispro within Lyumjev to Humalog, and their corresponding 90% CIs of the ratios using the mixed-effects model that includes treatment (Lyumjev, Humalog), sequence, period, and treatment as fixed effects and subject as a random effect. Analysis of iAUCs during the MMTT and AUCs during exercise will be based on untransformed endpoints, if negative values occurred. In this case, LSmeans, treatment differences in LSmeans, and corresponding 90% CIs for the treatment differences will be estimated from the model. The p-value on the difference between LSmeans will be used to determine statistical significance. The treatment ratios and 90% CIs for the ratios will be calculated using Fieller's theorem. Additionally, treatment differences in LSmeans, and corresponding 90% CIs may be estimated from the model for  $\Delta PG_{max}$ ,  $\Delta PG1h$ , and  $\Delta PG2h$  based on untransformed data.

The same model without log transformation will be used for the analysis of the rate of change in PG during the exercise period and exploratory GD time parameters. LSmeans, treatment differences in LSmeans, and the corresponding 90% CIs for the treatment differences will be estimated from the model. The p-value on the difference between LSmeans will be used to determine statistical significance. The treatment ratios and 90% CIs for the ratios will be calculated using the Fieller's theorem (Chow and Liu 2009).

Additionally, exploratory analysis may be conducted and will be defined in the SAP.

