The rate of change in PG during exercise period and exploratory GD time parameters will also be statistically analyzed. A mixed effect model will be used, identical to the one above, on the actual values of the parameters. The LS means, difference in LS means between Lyumjev and Humalog for corresponding basal rate reduction, and corresponding 90% CIs, as well as the p-value, will be reported. The treatment ratios and 90% CIs will be reported using Fieller's theorem.

Additionally, exploratory analysis may be conducted if deemed necessary upon review of the data.

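### The SAP adjusts the primary glucose change over exercise for 0-minute glucose but leaves the rate of change and the exercise AUC unadjusted, giving up precision without stating a reason

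*SAP*

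**What the plan says.** SAP 9.4.2 sets out three exercise analyses in turn.

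- **Primary endpoint, change in PG from start to end of exercise.** After four-level treatment, the terms are "sequence, period, timepoint, treatment-by-timepoint interaction as fixed effects, and participant-within-sequence as a random effect". Then: "Baseline (0 min timepoint) will be included as a covariate".
- **Secondary parameters, including the exercise AUC.** After four-level treatment, the terms are "sequence, and period as fixed effects, and participant-within-sequence will be included as a random effect". There is no baseline covariate and no timepoint. AUCs are log-transformed unless negative values occur.
- **Rate of change in PG during exercise.** "A mixed effect model will be used, identical to the one above, on the actual values of the parameters".

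Protocol 9.3.2.2.2 settles which model the last sentence points to: "The same model without log transformation will be used for the analysis of the rate of change in PG during the exercise period". There, the model just described is the secondary one, with no baseline term. The protocol's primary model (9.3.2.2.1) has no baseline term either, so at protocol level the two analyses used the same fixed effects.

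SAP 9.4.1 derives the primary change from the 0-hour sample taken before exercise starts. For the rate it says only "The rate of PG during the exercise, the nadir PG, decremental AUC, for each exercise assessments will be calculated", without a formula. An LS-mean difference, a 90% CI and a p-value are planned for both the change and the rate.

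**The concern.** If a participant completes the 60-minute session and the rate is end minus start over time, the rate is the primary change divided by 60. The trial would then analyse almost the same quantity twice, once adjusted for where glucose started and once not. Start glucose will vary between a participant's four sessions. If the fall in glucose depends on it, a chance difference in mean start glucose between the Lyumjev and Humalog sessions moves the unadjusted estimate and leaves the adjusted one largely untouched.

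Two things are at stake. The unadjusted exercise parameters are less precise than data already collected would allow. A reader may also find the product difference significant in one table and not in the next, with nothing in the SAP to explain it.

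**Working it through.** **1. The plan's own figure.** SAP 7 gives 28 completers, 14 mg/dL, SD 27.9 mg/dL, two-sided alpha 0.1 and about 80% power. Taking 27.9 as the SD of the within-participant Lyumjev-Humalog difference:

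- Normal approximation: n = (1.645 + 0.842)² × 27.9² / 14² = 24.6.
- Paired t-test: 80% power is reached at n = 26, and n = 28 gives 82.7%.

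This is close to the stated figure. Reading 27.9 as a per-period within-participant SD gives only 57% at n = 28. The paired-difference reading is therefore used below.

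**2. Inputs the documents do not give.** The slope of glucose change on start glucose is assumed to be -0.2 to -0.5. The within-participant SD of start glucose is assumed to be 15 to 25 mg/dL.

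**3. Half-width of the 90% CI for one product contrast at one basal reduction.** The within-participant variance of the change is 27.9²/2 = 389.2. With 28 participants in four periods, the residual df are 112 - 28 - 3 - 3 = 78 (77 with the covariate), so t = 1.665.

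- Unadjusted: 1.665 × √(2 × 389.2/28) = 1.665 × 5.27 = 8.78.
- Adjusted: replace 389.2 by 389.2 - (slope × SD)².

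| Slope | Start-glucose SD | Residual variance | SE | Half-width (mg/dL) |
|---|---|---|---|---|
| -0.2 | 15 | 380.2 | 5.21 | 8.68 |
| -0.2 | 25 | 364.2 | 5.10 | 8.49 |
| -0.5 | 15 | 333.0 | 4.88 | 8.12 |
| -0.5 | 25 | 233.0 | 4.08 | 6.79 |

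Simulation with the four SAP sequences and participant fitted as a block agrees: 8.7 to 8.8 unadjusted against 6.8 to 8.7 adjusted. At slope 0 it gives 8.76 against 8.82, so an unneeded covariate costs almost nothing.

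**4. How far apart the estimates are.** The gap is about slope × the difference in mean start glucose. The chance SD of that difference is SD × √(2/28), which is 4.0 mg/dL for SD 15 and 6.7 for SD 25. The simulated mean absolute gap is about 0.7 mg/dL (slope -0.2, SD 15) to 2.7 mg/dL (slope -0.5, SD 25). Both estimators average to the true difference in every scenario.

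**5. How often significance differs.** The contrast is Lyumjev against Humalog at 50% reduction, with true differences of 0 and 14 mg/dL and 2000 trials per setting. The ranges run over SD 15 and 25 and both true differences.

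| Slope | Opposite sides of p=0.10 |
|---|---|
| 0 | 1.6-2.1% |
| -0.2 | 2.4-5.2% |
| -0.4 | 4.4-10.2% |
| -0.6 | 8.2-14.5% |

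At a true 14 mg/dL, unadjusted against adjusted power is 83% against 84% (slope -0.2, SD 15) and 85% against 92% (slope -0.4, SD 25).

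**6. What these figures isolate.** Each trial fits the same single-timepoint change with and without the covariate. If every session lasts 60 minutes and rate = change/60, dividing by 60 rescales the estimate and SE together, so t and p are those of the matching change model. No AUC was simulated.

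**The case against.** The strongest reply is that the covariate is only one of the differences between the two analyses. The primary model also carries timepoint and treatment-by-timepoint terms. A reader might infer that 3% to 15% is the disagreement rate between the two SAP tables, or that adding the covariate would make them agree. Neither follows.

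A simulation that includes timepoint terms shows this. It assumed samples at 20, 40 and 60 minutes, errors that accumulate over time, slopes of 0 to -0.5, and 400 trials per setting. The primary 60-minute contrast and the rate as written disagreed in about 8% to 16% of trials. With the covariate added to the rate model they still disagreed in about 2.5% to 11%. At slope -0.2, SD 15 and a true 14 mg/dL, the covariate moved disagreement only from 8.8% to 7.5%. The sample times there are assumed, so the exact values are illustrative, but the point stands.

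Other parts also stand:

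- The rate has no formula and could be a regression slope. Exercise stops on hypoglycemia (protocol 4.1.3), so rate and total change separate in those sessions.
- A pre-exercise glucose target (protocol 4.1.3 and 5.2.1, item g) limits the spread of start glucose. Its range is redacted, so an SD of 25 cannot be checked.
- Rate and exercise AUC are not named in the objectives tables. Leaving supportive parameters unadjusted is a legitimate choice if it is stated.

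None of this explains why the SAP treats start glucose differently in the two models, or makes the lost precision useful.

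**Conclusion.** The inconsistency is in the text, and the consequence is moderate. Under the assumed slopes and start-glucose SDs, adjustment leaves the half-width for the change almost unchanged at the mild end and cuts it by about a fifth at the other (8.8 to 6.8 mg/dL). Significance differs in roughly 3% to 15% of trials when the covariate is the only difference. If the slope is zero, adjustment neither helps nor harms. The same logic applies to the exercise AUC, but its gain was not quantified and its scale may be logarithmic.

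Two further inferences are tempting. One is that the unadjusted rate analysis is biased. It is not: the issue is precision and chance imbalance. The other is that the covariate was simply not carried through when SAP version 2.0 updated the primary analysis. The SAP's document history records such an update, and Section 11 reports no changes from the protocol although the protocol's primary model has no baseline term. The documents do not show what version 1.0 contained or why the models differ, so this remains conjecture. The primary analysis and the sample size are unaffected.

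**What to change.** In SAP 9.4.2:

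1. Add 0-minute PG as a covariate to the mixed model for the rate of change in PG, and to the exercise (decremental) AUC model on whichever scale is analysed.
2. Define the rate as the change in PG divided by actual exercise duration, so that sessions stopped early are covered.
3. Keep the unadjusted models as sensitivity analyses. If the unadjusted form is preferred as the main one, give the reason.
4. Note that the primary model's timepoint terms can still produce a different p-value from the rate model.

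The cost is one degree of freedom per model and a sentence or so of SAP text. The 0-minute sample is already collected for the primary endpoint.
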